## **2 STUDY DESCRIPTION**

### **2.1 Study Design**

This is a multicenter, randomized, double-blind, placebo-controlled evaluation of the safety and efficacy of rimegepant 75 mg orally disintegrating tablet (ODT) taken every other day (EOD) for prophylaxis in adults with a history of inadequate response to a variety of available oral migraine-preventive medications from different mechanistic classes.

[figure not shown]

The study has 4 phases:

- Observation Phase (OP): Lasts approximately 28 days. Includes the Screening Visit and Pre-Randomization Evaluation Visit which must occur within 4 days of the Baseline Visit.
- DBT Phase:
  - Lasts up to 12 weeks, and includes the Baseline Visit, and Week 2, Week 4, Week 8, Week 12, and DBT EOT Visits.
  - Subjects are randomized 1:1 to 1 of the following 2 treatment groups at the Baseline Visit:
    - Rimegepant 75 mg dosed EOD
    - Placebo matching rimegepant 75 mg dosed EOD.
  - Randomization is stratified using a Randomization and Trial Supply Management (RTSM) system by (1) the number of migraine days reported to have occurred during the 28-day OP (4 to 7 or 8 to 14); and (2) the number of ROM medication categories with previous inadequate response (2 or 3 to 4). See Section 2.2.
    - Previous inadequate response is defined as lack of efficacy within 10 years of the Screening Visit, prior intolerance within 10 years of the Screening Visit, or contraindication.
  - All randomized subjects who discontinue early from the DBT Phase should complete the DBT EOT Visit. Otherwise, subjects should complete the Week 12 Visit.
- Open-label Extension (OLE) Phase:
  - Subjects who complete the DBT Phase and are in good standing may enter the OLE Phase. Subjects who (1) discontinue early from the DBT Phase or (2) have already entered the Follow-up Phase are not eligible to enter the OLE Phase.
  - Lasts up to 12 weeks, and includes the Week 14, Week 24, and OLE EOT Visits.
  - Subjects take rimegepant 75 mg dosed EOD.
  - All randomized subjects who discontinue early from the OLE Phase should complete the OLE EOT Visit. Otherwise, subjects should complete the Week 24 Visit.
- Follow-up Phase

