**Figure 1 Study Schematic**

## 2.2 Treatment Assignment

The RTSM system assigns a subject identifier number at the Screening Visit.

The RTSM system randomizes eligible subjects to treatment groups (see Section 2.1) using permuted blocks of size 6 within each of the 4 randomization strata at the Baseline Visit. Randomization is stratified by (1) the number of migraine days reported to have occurred during the 28-day OP (4 to 7 or 8 to 14); and (2) the number of ROM medication categories with previous inadequate response (2 or 3 to 4).

The RTSM system also assigns specific container numbers for study drug to be dispensed at the Baseline Visit and subsequent visits in the DBT and OLE Phases.

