## 4.3 Subgroups

Subgroup tables present results by subgroup level and overall for subjects with nonmissing subgroup level data. Subgroup levels may be redefined or combined based on the availability of data.

The following efficacy subgroups are of interest for the migraine analysis set (see Section 6.2.5.1):

- Imputed randomization stratum 1 – number of migraine days in the 28-day OP:  $<8$ ,  $\geq 8$
- Imputed randomization stratum 2 – number of ROM medication categories with previous inadequate response:  $<3$ ,  $\geq 3$
- Imputed 4-level randomization stratum:
  - $<8$  migraine days in the 28-day OP and  $<3$  ROM medication categories with previous inadequate response
  - $<8$  migraine days in the 28-day OP and  $\geq 3$  ROM medication categories with previous inadequate response
  - $\geq 8$  migraine days in the 28-day OP and  $<3$  ROM medication categories with previous inadequate response
  - $\geq 8$  migraine days in the 28-day OP and  $\geq 3$  ROM medication categories with previous inadequate response.

Medical history of hypertension is a safety subgroup of interest for hypertension-related safety endpoints for the DBT and OL rimegepant safety analysis sets (see Section 6.2.5.3). Refer to the Core SAP for the subgroup definition.

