## 5 SAMPLE SIZE, POWER, AND TYPE 1 ERROR

The study randomizes approximately 300 subjects per treatment group. Based on data from study C4951025 (BHV3000-305) and subgroup analysis from the galcanezumab Phase 3 program, we estimate that rimegepant provides roughly a 1.0-day advantage over placebo on the primary endpoint, and assuming a common standard deviation (SD) of 3.6 days. Assuming that roughly 280 subjects per treatment group contribute to the final migraine analysis dataset, the study has roughly 90% power on the primary endpoint at a 2-sided alpha level of 0.05.

In study C4951025 (BHV3000-305), rimegepant dosed EOD provided a 1.0-day advantage over placebo dosed EOD in subjects who were not taking prophylactic migraine medication through randomization. Using the data from study C4951025 (BHV3000-305), the SD of the primary endpoint was estimated to be roughly 3.6 days for these subjects.

Type 1 error is controlled using a 2-sided alpha level of 0.05 and hierarchical testing. First, the significance of the primary endpoint is evaluated at the 2-sided alpha level of 0.05 for rimegepant versus placebo. If the primary endpoint is not significant (i.e.,  $p\text{-value} > 0.05$ ), then any further tests on key secondary endpoints will have p-values presented only for descriptive purposes. If the primary endpoint is significant (i.e.,  $p\text{-value} \leq 0.05$ ), then the key secondary endpoints are tested hierarchically, each at a 2-sided alpha level of 0.05, in the order specified in Section 3.2.2.1. Thus, a key secondary endpoint is tested only if the preceding key secondary endpoint in the hierarchy is determined to be significant (i.e.,  $p\text{-value} \leq 0.05$ ). If a test in the hierarchy is not significant, then any further tests on endpoints in the sequence have p-values presented only for descriptive purposes, and no conclusions are drawn from those results.

For testing of other secondary or exploratory endpoints, no attempt is made to adjust for multiplicity. These endpoints are evaluated at an unadjusted, 2-sided alpha level of 0.05, and p-values are presented only for descriptive purposes.

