If the main analysis of the primary endpoint is not significant (i.e.,  $p\text{-value} > 0.05$ ), then any further tests of key secondary endpoints will have  $p$ -values presented only for descriptive purposes, and no conclusions are drawn from those results.

For a given treatment group comparison of a continuous endpoint, the null hypothesis of interest  $H_0$  is that the mean change observed on rimegepant (denoted  $\mu_{\text{rimegepant}}$ ) is equal to the one observed on placebo (denoted  $\mu_{\text{placebo}}$ ), i.e.,  $H_0: \mu_{\text{rimegepant}} = \mu_{\text{placebo}}$ . The alternative 2-sided hypothesis of interest  $H_1$  is that the mean changes observed on rimegepant and placebo differ, i.e.,  $H_1: \mu_{\text{rimegepant}} \neq \mu_{\text{placebo}}$ . For a given treatment group comparison of a binary endpoint, the hypotheses are based on percentages instead of mean changes.

The overall summary table of treatment comparisons of all primary and key secondary efficacy endpoints during the DBT Phase is also produced by subgroup level for all efficacy subgroups of interest described in Section 4.3. Separate tables are provided for each subgroup. Analyses of continuous endpoints are performed using models that exclude randomization stratum as a fixed effect, while analyses of binary endpoints are performed unstratified.  $P$ -values are presented only for descriptive purposes, and are not flagged for significance.

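### Subgroup analyses defined by one stratification factor also drop the other, so if that other factor is prognostic their descriptive intervals are somewhat wider than necessary

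*SAP*

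**What the plan says.** SAP 4.3 lists three efficacy subgroups for the migraine analysis set. One is imputed stratum 1, OP migraine days below 8 versus 8 or more. The second is "Imputed randomization stratum 2 – number of ROM medication categories with previous inadequate response", split at below 3 versus 3 or more. The third is the four-level combination of the two.

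SAP 2.2 says that the RTSM system randomizes "using permuted blocks of size 6 within each of the 4 randomization strata at the Baseline Visit", so both factors were used in blocking.

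The main model for migraine days (SAP 6.3.1.3, code in 9.3.1) has treatment, 4-level stratum, month and month-by-treatment. It has no continuous OP covariate, so the stratum is its only baseline adjustment. The MSQ and MIBS models (SAP 6.5.1 and 6.5.2) do carry a baseline score.

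For the subgroup tables of the primary and key secondary efficacy endpoints, SAP 6.3.2.3 gives one rule: "Analyses of continuous endpoints are performed using models that exclude randomization stratum as a fixed effect, while analyses of binary endpoints are performed unstratified". SAP 6.3 makes the same subgroup exception for binary endpoints. It also lets results be shown unstratified where a stratum is sparse, but the subgroup exception does not depend on sparseness. Subgroup p-values are descriptive and carry no significance flag.

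**The concern.** Within a level of the 4-level subgroup both factors are fixed, so there is no stratum left to adjust for and the rule is right. In a one-factor subgroup, two of the four strata are still present and differ on the other factor. Nothing in the SAP keeps that factor or says why it is removed.

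The ROM-category subgroups matter more. There the dropped factor is OP migraine frequency and the outcome is change from that same quantity. A subject with 4 to 7 OP days cannot improve by more than 7 days, whereas one with 8 to 14 can, so a link with the outcome is plausible.

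When allocation is balanced within levels of a prognostic factor, an analysis that ignores the factor overstates the standard error. The subgroup estimates would then be reported with too much uncertainty, and with a different adjustment from the main analysis beside them.

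**Working it through.** **Inputs from the documents (SAP 5 and 2.1).** Effect: "we estimate that rimegepant provides roughly a 1.0-day advantage over placebo on the primary endpoint". SD: "assuming a common standard deviation (SD) of 3.6 days". Numbers: "Assuming that roughly 280 subjects per treatment group contribute to the final migraine analysis dataset". Allocation: "Subjects are randomized 1:1 to 1 of the following 2 treatment groups at the Baseline Visit".

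**Reproducing the plan's own figure.** SE = 3.6 × sqrt(2/280) = 0.304. Power = Φ(1.0/0.304 − 1.96) = 0.908. This agrees with the statement that "the study has roughly 90% power on the primary endpoint at a 2-sided alpha level of 0.05", so the inputs are read correctly.

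**Assumptions not in the documents.** The subgroup is half of 280, so n = 140 per arm. The remaining factor splits the subgroup with share q in one level. Mean change differs between its levels by D days. The SD of 3.6 is the within-subgroup SD. There is no treatment-by-factor interaction.

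**Continuous endpoints.**
- Unadjusted 95% half-width = 1.96 × 3.6 × sqrt(2/140) = 0.843 days.
- Share of variance explained by the dropped factor: R² = q(1−q)D²/3.6².
- Adjusted half-width = 0.843 × sqrt(1 − R²).
- Example, q = 0.5 and D = 2: R² = 0.25 × 4/12.96 = 0.077, and 0.843 × sqrt(0.923) = 0.810.

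| D (days) | R², q = 0.5 | Adjusted half-width | Narrower by, q = 0.5 | Narrower by, q = 0.3 |
|---|---|---|---|---|
| 0 | 0 | 0.843 | 0% | 0% |
| 1 | 0.019 | 0.835 | 1.0% | 0.8% |
| 2 | 0.077 | 0.810 | 3.9% | 3.3% |
| 3 | 0.174 | 0.767 | 9.1% | 7.6% |

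The percentages do not depend on subgroup size. The unadjusted half-width is 1.089 at 84 per arm and 0.713 at 196 per arm.

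**What D might be for OP frequency (illustration only).** If OP days were uniform on 4 to 14, the level means would be 5.5 and 11, with shares 4/11 and 7/11. Equal proportional reductions of 30%, 40% and 50% in both levels give D = 5.5 × 0.3, 0.4 and 0.5 = 1.65, 2.2 and 2.75 days. The same formula with q = 4/11 gives 2.5%, 4.4% and 7.0% narrower.

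**Simulation check.** 3,000 runs, 140 per arm, blocks of 6 within two equal levels, sandwich SE, one observation per subject (so not the full three-month model).

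| D | Mean SE, unadjusted | Mean SE, adjusted | Ratio | Coverage, unadjusted | Coverage, adjusted |
|---|---|---|---|---|---|
| 0 | 0.428 | 0.427 | 0.998 | 95.3% | 95.3% |
| 1 | 0.428 | 0.423 | 0.988 | 94.9% | 94.7% |
| 2 | 0.429 | 0.411 | 0.959 | 95.6% | 94.9% |
| 3 | 0.429 | 0.389 | 0.907 | 96.1% | 93.9% |

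At D = 3 the empirical SD of the estimate was 0.399 with or without adjustment. Blocking has already balanced the factor, so what changes is the reported SE. The Monte Carlo error on coverage is sqrt(0.95 × 0.05/3000) = 0.4 points. The adjusted coverage of 93.9% at D = 3 is therefore a little low, and the full 9% should not be read as entirely free.

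**Binary endpoints.** Illustrative overall response of 30% versus 40%, 140 per arm, equal levels. Unstratified half-width = 1.96 × sqrt((0.3 × 0.7 + 0.4 × 0.6)/140) = 11.1 points. With a 30-point gap between levels (45% and 15% on placebo, 55% and 25% on rimegepant), the stratified half-width is 1.96 × sqrt(0.5 × (0.2475 + 0.1275 + 0.2475 + 0.1875)/140) = 10.5 points, 5.1% narrower. Gaps of 0, 10 and 20 points give 0%, 0.6% and 2.3%.

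**The case against.** The strongest reply is that nothing inferential depends on this. The subgroup p-values are descriptive and sit outside the hierarchy, and the primary and key secondary efficacy tests keep the 4-level stratum. One simple rule across three tables is openly stated and avoids sparse cells. The documents give no prognostic strength for either factor, so the loss could be zero. A 9% gain needs a gap between levels three times the planned treatment effect. For ROM category within the OP-frequency subgroups there is no particular reason to expect a gain.

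All of that limits the size of the point, and it stands. It does not show a disadvantage in keeping the factor. Sparseness is already covered by the fallback in SAP 6.3.

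A reader might infer three stronger things that the documents do not support:
- **Bias or inflated type 1 error.** Randomization was balanced within strata, and in the simulation the unadjusted interval was, if anything, conservative.
- **Lost power.** The plan draws no conclusion from subgroup tests, so a power comparison would describe a decision that nobody takes.
- **Damage to a stated objective.** The primary objective concerns the whole population with inadequate response across 2 to 4 categories. No objective in SAP 3.1 compares fewer than 3 with 3 or more.

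**Conclusion.** The point holds as a minor matter of precision. SAP 6.3.2.3 and 6.3 remove more than they need to in the two one-factor subgroups, and the ROM-category models for migraine days are left without any adjustment for OP migraine frequency.

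Whether the intervals are wider than necessary depends on prognostic strength, which has to be assumed. Under the assumptions above, the range is from nothing to about 9% for continuous endpoints, and from nothing to about 5% in the binary example. Gaps of 1 to 2 days give 1% to 4%. Any gain is likelier in the ROM-category subgroups than in the OP-frequency subgroups. For the 4-level subgroup the plan is correct as written.

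**What to change.** Amend SAP 6.3.2.3, and the subgroup exception in SAP 6.3, to say:
- ROM-category subgroups: keep imputed stratum 1.
- OP-frequency subgroups: keep imputed stratum 2.
- In both, use the kept factor as a two-level fixed effect for continuous endpoints and as the Mantel-Haenszel stratum for binary endpoints. The SAP 6.3 fallback to unstratified results applies where data are sparse.
- 4-level subgroup: no stratum term.

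The cost is a sentence in the SAP and one changed model or strata statement for each affected table. No new data are needed and error control is untouched. The change should be in place before treatment is unblinded at the PCD database lock.

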### **6.3.3 Exploratory Efficacy Endpoints**

#### **6.3.3.1 Headache Days per Month Changes From OP Over Time on DBT**

The number of headache days per month are prorated to 28 days and defined analogously to migraine days per month (see Section 6.3.1).

A headache day is defined in Section 9.2.6.

Analyses are based on the migraine analysis set with eDiary efficacy data dates in the OP and on-DBT efficacy analysis periods (see Section 7.2).

### **Descriptive Analyses**

The table of values and changes (both absolute and percent) from the OP in the number of headache days per month in the DBT Phase is provided, and has the same format as the one described in Section 6.3.1.2.

In the percent change analyses, subjects must also have  $\geq 1$  headache day (absolute not prorated) of appropriate pain intensity in the OP analysis period to be included.

### **Treatment Group Comparisons**

Treatment groups are compared using a model with the same attributes as the one for the primary endpoint except that change from the OP in number of total headache days per month is the dependent variable. The table has the same format as the one described in Section 6.3.1.3.

These analyses are repeated for moderate or severe headache pain intensity. All variables in the model are the same, except change from the OP in number of moderate or severe headache days per month is the dependent variable. The table has the same format.

Results support exploratory objective #1.

#### **6.3.3.2      *Percentages of Subjects With Reductions From OP in Number of Headache Days per Month Over Time on DBT***

Analyses are based on the migraine analysis set with eDiary efficacy data dates in the OP and on-DBT efficacy analysis periods (see Section 7.2). The percentage of subjects with reduction in the number of headache days during the DBT Phase is defined and assessed analogously to the percentage of subjects with reduction in the number of migraine days during the DBT Phase (see Section 6.3.2.1).

### **Treatment Group Comparisons**

For each pain intensity (total; moderate or severe) and select percentage reduction ( $\geq 30\%$ ,  $\geq 50\%$ ,  $\geq 75\%$ , and  $100\%$ ), the percentages of subjects with reduction in the number of headache days per month are compared between rimegepant and placebo using Mantel-Haenszel risk estimation with stratification by 4-level randomization stratum. Percentages are calculated against the number of subjects in the migraine analysis set at all time points.

The table has the same format as the one described in Section 6.3.2.1 at each month of the DBT Phase and overall DBT by headache pain intensity.

Results support exploratory objective #2.

#### **6.3.3.3      *Migraine Days per Week and Headache Days per Week Changes From OP Over Time in the First Month on DBT***

The number of migraine days per week in the first month (Weeks 1 to 4) of the DBT Phase is examined relative to the number of migraine days per week in the OP for the first month migraine analysis set, i.e., subjects in the DBT efficacy analysis set with  $\geq 24$  days of eDiary efficacy data (not necessarily consecutive) in both the OP analysis period and first month of the on-DBT efficacy analysis period.

Weeks 1 to 4 of the DBT Phase are defined as follows:

- Week 1: study days 1 to 7
- Week 2: study days 8 to 14
- Week 3: study days 15 to 21
- Week 4: study days 22 to 28.

See Sections 7.2 and 7.3 for the definition of analysis periods and study days used to define analysis visit windows.

Analyses are based on the first month migraine analysis set using eDiary efficacy data dates in the OP and on-DBT efficacy analysis periods.

The number of migraine days per week is prorated to 7 days and derived as follows:

- OP:  $7 \times (\text{total number of migraine days in the OP analysis period}) / (\text{total number of eDiary efficacy data days in the OP analysis period})$
- Week (7-day interval) of the on-DBT efficacy analysis period:  $7 \times (\text{total number of migraine days in the week}) / (\text{total number of eDiary efficacy data days in the week})$ .

The number of headache days per week is derived analogously.

### Descriptive Analyses

The table of values and changes (both absolute and percent) from the OP in the number of migraine days per week in the first month (Weeks 1 to 4) of the DBT Phase is provided, and summarizes parameters descriptively as continuous variables (including 2-sided normal 95% CIs for mean change) by treatment group and headache pain intensity (total; moderate or severe). In the percent change analyses, subjects must also have  $\geq 1$  migraine day of appropriate intensity (absolute not prorated) in the OP analysis period to be included.

The table of values and changes from the OP in number of headache days per week in the first month of the DBT Phase is provided analogously.

### Treatment Group Comparisons

Treatment groups are compared using a linear mixed effects model with repeated measures and the following attributes:

- Variables: change from the OP in number of total migraine days per week as the dependent variable; treatment group, 4-level randomization stratum, categorical week (i.e., Weeks 1 to 4 of the DBT Phase), and the week-by-treatment group interaction as fixed effects.
- Covariance structure for repeated measures accounting for within-subject correlated errors: see Section 6.3.1.3.
- SE estimation method: see Section 6.3.1.3.

The table displays the following model estimates:

- LSM change from OP, SE, and 95% CI by week for each treatment group
- Difference in LSM changes from OP between rimegepant and placebo (rimegepant – placebo), SE, 95% CI, and p-value for each week.

See Section 9.3.1 for example SAS code.

These analyses are repeated for moderate or severe headache pain intensity. All variables in the model are the same, except change from the OP in number of moderate or severe migraine days per week is the dependent variable. The corresponding table has the same format.

All analyses described above are performed analogously for headache days per week.

Results support exploratory objective #3.

#### **6.3.3.4      *Percentages of Subjects With Reductions From OP in Numbers of Migraine Days per Week and Headache Days per Week Over Time in the First Month on DBT***

Analyses are based on the first month migraine analysis set with eDiary efficacy data dates in the OP and on-DBT efficacy analysis periods (see Section 7.2).

In analyses of migraine days per week, subjects must (1) achieve the reduction criterion from OP in the number of migraine days in the specified week, and (2) have  $\geq 1$  migraine day (absolute not prorated) of appropriate pain intensity in the OP analysis period to be classified as responders in the specified week. Otherwise, subjects are classified as failures in the specified week.

Headache day analyses by week are defined analogously to migraine day analyses by week.

### **Treatment Group Comparisons**

For each headache pain intensity (total; moderate or severe), the percentages of subjects with  $\geq 50\%$  reduction in the number of migraine days per week are compared between rimegepant and placebo using Mantel-Haenszel risk estimation with stratification by 4-level randomization stratum. Percentages are calculated against the number of subjects in the first month migraine analysis set at all time points.

The table displays the following statistics at each week of the DBT Phase by headache pain intensity:

- Response rate (i.e., “n/N” and percentage), ASE, and 95% CI for each treatment group
- Stratified percentage difference between rimegepant and placebo (rimegepant – placebo), ASE, 95% CI, and p-value.

All analyses described above are performed analogously for headache days per week.

Results support exploratory objective #4.

